6.10.3. Pharmacodynamic Assessments

The relationship between C_{max} , AUC and other PK parameters with efficacy assessments (Section 6.10.1) will be explored as appropriate.

6.10.4. Blood Sample Collection, Storage and Shipping

Sample collection, storage and shipment procedures for clinical laboratory samples are provided in the Laboratory Manual.

7. STUDY ACTIVITIES

During the study, blood samples for hormones should be collected between 6-10 AM (06:00-10:00), as close to 8 AM (08:00) as practicable. Early morning saliva samples should be collected 30-45 minutes after awakening for the day. Late night saliva samples should be collected between 10 PM and 12 AM (22:00-00:00). Within this protocol, references to the study day of a 24-hr UFC collection mean that the collection was to have begun on that study day (e.g., a “Day 14” 24-hr UFC is one that was to have begun on Day 14 and completed on Day 15). All sample collections and study visits and procedures from Visit T1 to Visit R3/A3/ET have a window of + 2 days. All other sample collections, study visits, and procedures have a window of ± 7 days.

Study visit designations (S1, T1, etc.) are shown in the detailed schedule of study assessments presented in [Appendix 1](#).

7.1. Screening Visit, Visit S1

The screening visit should be conducted within 56 days (8 weeks) prior to enrollment into the open-label dose-escalation period. The date of screening is considered to be the date that the first study-related screening assessment is performed. At screening, appropriate study site personnel should:

- Obtain and document informed consent from the subject prior to any study procedures being performed.
- Assign a study-specific subject number.
- Contact the IVRS/IWRS to register the subject in the study
- Obtain and record medical history, demographic data and prior and current medications.
- Record vital signs, height and weight.
- Perform a complete PE.
- Obtain a 12-lead ECG.
- Collect fasting blood samples for hematology, chemistry, PT, aPTT, INR, insulin, HbA1c, lipid panel, HBsAg, HCV, HIV, hormones (11-DOC, 17-OHP, A, A4, ACTH, cortisol, DHEA, DHEAS, free T, P, renin, SHBG and total T) and serum pregnancy test.
 - Note: Subjects who require wash-out of medications that affect cortisol levels should NOT have their hormone levels drawn at S1. Instead, they should complete the required wash-out and return to the site for hormone levels later during the screening period.
 - All blood hormone collections should be performed between 6-10 AM (06:00-10:00), as close to 8 AM (08:00) as practicable.
 - Subjects need to be in a seated position for at least 15 minutes prior to collection of blood hormone levels so that renin and aldosterone levels are stable.
 - If the subject is not fasting, proceed with the visit but mark the sample collection as being non-fasting.

- Collect a urine sample for urinalysis and urine drug screen.
- Review all assessable inclusion and exclusion criteria.
- Provide instructions to the subject regarding 24-hr urine samples and early morning (30-45 minutes after awakening for the day) and late night (10 PM-12 AM; 22:00-00:00) saliva samples to be collected at home prior to the next visit.
 - During the screening period, subjects must perform two 24-hr urine collections, two early morning saliva collections and two late night saliva collections within 28 days prior to enrollment into the open-label dose-escalation period (Visit T1). The two early morning collections should be done on different days from each other, as should the two late night collections. These samples need to be submitted to the central laboratory for processing in time for results to be reviewed for eligibility prior to enrollment.
 - Per subject preference, these samples may be brought to the study site, or a visiting nurse may assist with processing the samples and shipping them to the central laboratory.
 - Subjects who require wash-out of medications should perform these collections AFTER wash-out.
- Schedule the next study visit (Visit T1) so that the blood hormone sample collections for that visit will occur as close to 8 AM (08:00) as practicable and between 6-10 AM (06:00-10:00).

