6. STUDY PROCEDURES

Subjects need to be fasting after 10 PM (22:00; water and maintenance medications allowed) the evening prior to Visits S1, R1/A1, and R3/A3/ET to allow for collection of the fasting lipid panel, glucose and insulin (if the subject is not fasting, proceed with the visit but mark the sample collection as being non-fasting). All blood hormone collections should be performed between 6-10 AM (06:00-10:00), as close to 8 AM (08:00) as practicable. All early morning saliva collections should be performed 30-45 minutes after awakening for the day. All late night saliva collections should be performed between 10 PM-12 AM (22:00-00:00).

If applicable (i.e., Visits T2 to R3/A3/ET), subjects should take their evening dose of study drug the evening prior to study visits (and also note the approximate time of the dose). On the morning of Visits T1 to R2/A2, subjects should wait to take their morning dose of study drug until directed by site personnel at the study site.

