6.3. Eligibility

Review of study inclusion/exclusion criteria will be done at/after the screening visit (Visit S1), before enrolling the subject into the open-label dose-escalation period at Visit T1 and before either randomizing the subject or enrolling the subject into the additional open-label dosing period at Visit R1/A1. Please note that prior to enrolling the subject into the open-label dose-escalation period, regarding the laboratory values, only the Visit T1 pregnancy test (if applicable and if performed at the site), and the Visit S1 hematology, chemistry, PT, PTT, INR, HbA1c, lipid panel, serology, pregnancy test (if applicable), urinalysis, urine drug screen, 24-hr UFC, and salivary cortisol levels need to be reviewed. The screening blood hormone levels are for baselining purposes and the results do not need to be available prior to enrolling the subject.

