6.5. Prior and/or Concomitant Medication Assessments

Prior and concomitant medications that should be recorded include any treatments taken from screening (Visit S1) until the end of the study/end of trial (Visit F1), as well as any radiotherapy for Cushing's syndrome performed at any time prior to screening and any treatments for Cushing's syndrome taken within the year prior to screening. Any treatments given during the study other than ATR-101, including blood transfusions, parenteral fluids and herbal preparations, are considered to be concomitant therapies and must be recorded on the eCRF.

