6.10.1.4. Glucose, Insulin and HbA1c

Subjects need to be fasting after 10 PM (22:00; water and maintenance medications allowed) the evening prior to Visits S1, R1/A1, and R3/A3/ET to allow for determination of fasting glucose and fasting insulin levels. Fasting glucose, insulin and HbA1c will be measured at the central laboratory using validated methods for these visits and used for calculations of insulin sensitivity. Further details on sample collection and handling are provided in the Laboratory Manual.

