6.10.1.5. Lipid Panel

Subjects need to be fasting after 10 PM (22:00; water and maintenance medications allowed) the evening prior to Visits S1, R1/A1, and R3/A3/ET to allow for collection of the fasting lipid panel. Fasting lipids (total cholesterol, LDL, HDL and triglycerides) will be measured at the central laboratory using validated methods for these study visits. Further details on sample collection and handling are provided in the Laboratory Manual.

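### Subjects who finish a wash-out during screening have no fasting insulin or lipid sample between the end of wash-out and the first dose of ATR-101

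*Protocol*

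**What the plan says.** Section 3.1.1 places any wash-out of Cushing's medication inside a screening period of up to 8 weeks. Section 7.1 allows S1 up to 56 days before enrollment. Every subject gives a fasting sample at S1 that includes chemistry, insulin, HbA1c and the lipid panel.

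Section 7.1 makes one exception for wash-out: "Subjects who require wash-out of medications that affect cortisol levels should NOT have their hormone levels drawn at S1". Those subjects return after wash-out, for hormone levels only. Sections 6.10.1.1 and 6.10.1.2 defer UFC and saliva in the same way. Section 6.3 explains the purpose of the hormone samples: "The screening blood hormone levels are for baselining purposes and the results do not need to be available prior to enrolling the subject".

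For the metabolic panel, Section 6 requires fasting "the evening prior to Visits S1, R1/A1, and R3/A3/ET to allow for collection of the fasting lipid panel, glucose and insulin". Section 6.10.1.4 says glucose, insulin and HbA1c are "measured at the central laboratory using validated methods for these visits and used for calculations of insulin sensitivity", and Section 6.10.1.5 says "Fasting lipids (total cholesterol, LDL, HDL and triglycerides) will be measured at the central laboratory using validated methods for these study visits". The visits meant are again S1, R1/A1 and R3/A3/ET. Table 6 marks the insulin, HbA1c and lipid row once, at S1.

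Section 7.2.1 (T1, Day 1) lists hematology, chemistry, hormones and PK before the first dose. It lists no insulin or lipids and asks for no fast. Section 9.6.1.2 names the change from baseline in fasting glucose, insulin and lipid panel as a secondary efficacy endpoint.

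**The concern.** The protocol recognises that samples drawn on the earlier drug are unsuitable as a baseline, and it protects hormones, UFC and saliva accordingly. Fasting insulin and lipids, which also feed a change-from-baseline endpoint, get no such protection.

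An affected subject's baseline can be taken on the earlier treatment or before its wash-out is complete, while the Day 57 and Day 85 values are taken off that drug and after ATR-101. The open-label change has no control arm to absorb the difference. Its direction depends on what was stopped: the Section 5.12 list includes cortisol-lowering drugs, PPAR-gamma agonists and fenofibrate, which need not all act the same way on insulin and lipids.

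**Working it through.** **Scheduled samples before the first dose**

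| Sample | S1 | Return after wash-out | T1 |
|---|---|---|---|
| Blood hormones | only if no wash-out is needed | yes | yes |
| Fasting insulin, lipids | yes, all subjects | no | no |
| Glucose (in chemistry) | yes, fasting | no | yes, no fast required |
| Blood pressure, weight | yes | no | yes |

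T1 glucose comes without insulin, so S1 is the only pre-dose source for the insulin-sensitivity calculation in Section 6.10.1.4.

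**Can S1 fall on prior treatment?** Section 5.12 counts wash-outs back from Day -14, so the latest last dose is Day (-14 minus wash-out days). Exclusion criterion 7 counts back from the first screening UFC, and Section 5.12 also requires wash-out before hormone and UFC collection. The UFCs may start as early as Day -28. With S1 at Day -56:

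| Drug group | Wash-out (days) | Latest last dose, Day -14 anchor | Days after S1 | Latest last dose, Day -28 anchor | Days after S1 |
|---|---|---|---|---|---|
| Dopamine agonists, PPAR-gamma agonists, pasireotide | 28 | -42 | 14 | -56 | 0 |
| Mifepristone | 21 | -35 | 21 | -49 | 7 |
| Ketoconazole, metyrapone, immediate-release octreotide | 7 | -21 | 35 | -35 | 21 |
| Fenofibrate | 5 | -19 | 37 | -33 | 23 |

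Under either anchor an S1 sample at Day -56 can be drawn on treatment. The long wash-outs differ. On the Day -14 anchor the 14-week drugs must have stopped at least 98 + 14 - 56 = 56 days before that S1, and mitotane at least 182 + 14 - 56 = 140 days before it. For these, S1 falls part-way through wash-out or after it.

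**Illustrative size.** The protocol gives no share or shift, so both are assumed. Let f be the share of analysed subjects whose wash-out ends after S1, and d the shift from stopping, in SDs of the within-subject change and in one common direction. Bias = f × d.

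| d | f = 0 | f = 0.25 | f = 0.50 |
|---|---|---|---|
| 0.25 | 0 | 0.0625 | 0.125 |
| 0.50 | 0 | 0.125 | 0.25 |
| 1.00 | 0 | 0.25 | 0.50 |

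At d = 0.5, coverage of a nominal 95% one-sample t interval follows from the noncentral t distribution with noncentrality f × d × √n:

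| n | f = 0 | f = 0.25 | f = 0.50 |
|---|---|---|---|
| 16 (15 df; bias 0, 0.5, 1 SE) | 95% | 92.4% | 84.5% |
| 8 (7 df; bias 0, 0.35, 0.71 SE) | 95% | 93.9% | 90.6% |

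Here n = 16 is all enrolled subjects and so an upper limit. By default Section 9.6.1.2 uses the ITT population, which Section 9.3 restricts to randomized and dosed subjects. Its size is not given, and n = 8 is an assumption.

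**Cost of excluding the affected subjects instead.** The SE rises by 1/√(1 - f) - 1, which is 15.5% at f = 0.25 and 41.4% at f = 0.50.

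**The case against.** The strongest reply is that the gap is possible rather than certain, and narrow.

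- **Timing.** The ±7-day window for screening assessments (Section 6.1) could let a wash-out of 4 to 7 days finish before the S1 draw, and the offsets above take S1 at its earliest. This stands as a limit on how many subjects are affected. Nothing, however, requires the draw to follow wash-out, and a return visit for hormones alone implies that the other S1 samples come earlier.
- **Stable background treatment.** Section 5.12 keeps anti-lipid drugs at the screening dose and limits changes in antidiabetic drugs. That removes some confounding, but does not cover stopping the listed Cushing's drugs, PPAR-gamma agonists or fenofibrate.
- **Glucose.** T1 blood is drawn before breakfast, so a SAP could use T1 glucose as the baseline. This is fair, although no fast is required. It does not help insulin or lipids.
- **SAP remedy.** Section 6.5 records "any treatments taken from screening (Visit S1) until the end of the study/end of trial (Visit F1", so affected subjects can be identified and set apart. They still have no off-treatment baseline.
- **The coverage figures.** The protocol specifies no one-sample t interval, only ANCOVA or ANOVA as appropriate. The formula also ignores the variance that a mixture of shifted and unshifted subjects adds. Simulation with that variance gives about 93.1% and 85.9% at n = 16 in place of 92.4% and 84.5%, so the stated loss is slightly too large. Opposing shifts would partly cancel.
- **A narrower remedy.** The panel could be drawn at the post-wash-out return visit, for affected subjects only. That is workable, but the return visit is written for drugs that affect cortisol, so it may miss others such as fenofibrate. It would also leave baselines taken at different points.

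**Conclusion.** The concern holds, as a minor point. The schedule gap is plain in the text: for subjects whose wash-out ends after S1, no fasting insulin or lipid sample is planned off the earlier drug and before ATR-101.

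The harm falls on the uncontrolled open-label change in fasting insulin and lipids, and in fasting glucose if S1 is its baseline. The size is unknown and possibly zero. Over assumed shifts of 0.25 to 1.0 SD the bias is 0.06 to 0.25 SD if 25% are washed out, and 0.13 to 0.50 SD if 50% are. These figures rest on a common direction of shift and on shares the protocol does not give.

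Not affected are the primary UFC endpoint, blood pressure, BMI, and subjects who need no wash-out or completed it before S1. The randomized comparison is largely unaffected, because R1 supplies a fasting sample at randomization.

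**What to change.** Make T1 a fasting visit for all subjects and add insulin and the lipid panel to its existing pre-dose draw. Mark non-fasting samples as is already done at S1 and R1.

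Name the T1 sample as the baseline for fasting glucose, insulin and lipids. Allow S1 as a fallback only if T1 is missing or non-fasting and the subject needed no wash-out or had completed it before S1. A washed-out subject with a non-fasting T1 would then still lack a valid baseline, so the reminder matters. It belongs in Section 7.1 at the instruction "Schedule the next study visit (Visit T1) so that the blood hormone sample collections for that visit will occur".

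The places to edit are Sections 6, 6.10, 6.10.1.4, 6.10.1.5, 7.1 and 7.2.1, and Table 6 with its footnote c.

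The cost is extra tubes and one fasting reminder, plus the amendment and IRB/EC step in Section 10.17. No visit is added, and T1 already runs draw, breakfast, then dose, as R1 does. The S1 tests stay in place for eligibility. Enrollment need not wait for the new results, since Section 6.3 requires, among T1 laboratory values, "only the Visit T1 pregnancy test (if applicable and if performed at the site"). No dose, wash-out length or clinical rule changes.

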7.2. Open-label Dose-escalation Period

Only subjects who meet all of the inclusion criteria and none of the exclusion criteria should be enrolled and enter the 8-week open-label dose-escalation period. During the open-label dose-escalation period, subjects will take their assigned study drug and undergo assessments to evaluate efficacy, safety, tolerability and PK of study drug. At Visit T1, all subjects will initially be assigned to take ATR-101 250 mg BID. After 2 weeks, at Visit T2, all subjects will be assigned to take the next higher dose of ATR-101, 500 mg BID. After 2 additional weeks, at Visit T3, all subjects will be assigned to take the next higher dose of ATR-101, 1000 mg BID. At any time, the ATR-101 dose may be down-titrated as needed for safety reasons at the discretion of the Investigator.

7.2.1. Visit T1 (Day 1)

At Visit T1, appropriate study site personnel should:

- Record adverse events and update medications.
- Record vital signs and weight.
- Perform a complete PE.
- Collect a urine sample for urinalysis and, if the subject is a woman of childbearing potential, perform a urine pregnancy test (preferred; or submit a serum or urine sample to a laboratory for pregnancy testing if required by your institution/IRB/EC).
- Review all inclusion and exclusion criteria to confirm that the subject is eligible for the study, including all 24-hr UFC and late night salivary cortisol levels collected within the past 28 days.

- Review the mean of all 24-hr UFC levels obtained within the past 28 days to determine the subject's 24-hr UFC stratum (1.3 to $< 4 \times$ ULN (Stratum I) or 4 to $10 \times$ ULN (Stratum II)).
- Please note that prior to enrolling the subject, regarding the laboratory values, only the Visit T1 pregnancy test (if applicable and if performed at the site), and the Visit S1 hematology, chemistry, PT, PTT, INR, HbA1c, lipid panel, serology, pregnancy test (if applicable), urinalysis, urine drug screen, 24-hr UFC, and salivary cortisol levels, need to be reviewed. The screening blood hormone levels are for baselining purposes and the results do not need to be available prior to the enrolling the subject.
- Contact the IVRS/IWRS to confirm enrollment of the subject into the open-label dose-escalation period and obtain study drug assignment.
- Collect blood samples for hematology, chemistry, hormones (11-DOC, 17-OHP, A, A4, ACTH, cortisol, DHEA, DHEAS, free T, P, renin, SHBG and total T) and PK within 30 minutes prior to administration of study drug.
 - All blood hormone collections should be performed between 6-10 AM (06:00-10:00), as close to 8 AM (08:00) as practicable.
 - Subjects need to be in a seated position for at least 15 minutes prior to collection of blood hormone levels so that renin and aldosterone levels are stable.
- Dispense open-label study drug (ATR-101 250-mg tablets) and instruct the subject on self-administration of study drug orally with food BID.
- Have the subject eat breakfast.
- Ask the subject to self-administer study drug with a nonalcoholic beverage (except grapefruit juice) while at the study site. Record the exact time of study drug administration.
- Collect plasma PK samples 1, 2, 3 and 4 hrs after administration of study drug. Record the exact time of each PK sample collection.
- Provide instructions to the subject regarding 24-hr urine samples and saliva samples to be collected at home prior to the next visit (Section [7.2.2](#)).
- Schedule the next study visit (Visit T2) so that the blood hormone sample collections for that visit will occur as close to 8 AM (08:00) as practicable and between 6-10 AM (06:00-10:00).
- Remind the subjects that they will need to record the approximate time of their evening study drug dose prior to their next visit.
- Remind the subjects that on the morning of their next visit, they should wait to take their morning dose of study drug until directed by site personnel at the study site, and they will need to bring the 24-hr urine and saliva samples collected on or prior to Day 14 to the study site.

7.2.2. Between Visits T1 and T2, Between Visits T2 and T3 and Between Visits T3 and R1/A1

On Days 13, 14, 27, 28, 41, 42, 50, 51, and 56 during the open-label dose-escalation period, subjects should:

- Collect an early morning saliva sample.
- Collect a late night saliva sample.
- Begin a 24-hr urine collection.

In addition, at the indicated study days during the open-label dose-escalation period, subjects should:

- Days 14, 28 and 56 (the day prior to Visits T2, T3 and R1/A1, respectively): Record the approximate time of the evening study drug dose.
- Days 15, 29, and 57 (the day of Visits T2, T3, and R1/A1, respectively): Take any collected saliva samples and 24-hr urine samples (i.e., the Day 13/14, 27/28, and 56 saliva samples and 24-hr urine samples, respectively; and any other saliva samples and urine samples that were not previously submitted) to the study site.
- Days 43 and 52: Take the 24-hr urine collection and any collected saliva samples to the study site, or a visiting nurse will assist with processing the samples and shipping them to the central laboratory, per subject preference.
- Day 56 (the evening prior to Visit R1): Fast after 10 PM (22:00; water and maintenance medications allowed).

7.2.3. Visit T2 (Day 15)

At Visit T2, appropriate study site personnel should:

- Receive the Day 13 and Day 14 saliva collections and 24-hr urine collections from the subject and submit these to the central laboratory for analysis.
- Record adverse events and update medications.
- Record vital signs and weight.
- Perform a brief PE, with particular attention to assessing the subject for possible adrenal insufficiency.
- Collect blood samples for hematology, chemistry, hormones (11-DOC, 17-OHP, A, A4, ACTH, cortisol, DHEA, DHEAS, free T, P, renin, SHBG and total T) and PK within 30 minutes prior to administration of study drug.
 - All blood hormone collections should be performed between 6-10 AM (06:00-10:00), as close to 8 AM (08:00) as practicable.
 - Subjects need to be in a seated position for at least 15 minutes prior to collection of blood hormone levels so that renin and aldosterone levels are stable.
- If the subject is a woman of childbearing potential, collect a urine sample and perform a urine pregnancy test (preferred; or submit a serum or urine sample to a laboratory for pregnancy testing if required by your institution/IRB/EC).
- Record the date and time of the subject's last previous study drug dose (expected to have occurred the evening prior to the visit).

- Collect study drug and assess compliance.
- Contact IVRS/IWRS to obtain study drug assignment.
- Dispense open-label study drug (ATR-101 500-mg tablets) and instruct the subject on self-administration of study drug orally with food BID.
- Have the subject eat breakfast.
- Ask the subject to self-administer study drug with a nonalcoholic beverage (except grapefruit juice) while at the study site. Record the exact time of study drug administration.
- Collect plasma PK samples 1, 2, 3 and 4 hrs after administration of study drug. Record the exact time of each PK sample collection.
- Provide instructions to the subject regarding 24-hr urine samples and saliva samples to be collected at home prior to the next visit (Section 7.2.2).
- Schedule the next study visit (Visit T3) so that the blood hormone sample collections for that visit will occur as close to 8 AM (08:00) as practicable and between 6-10 AM (06:00-10:00).
- Remind the subjects that they will need to record the approximate time of their evening study drug dose prior to their next visit.
- Remind the subjects that on the morning of their next visit, they should wait to take their morning dose of study drug until directed by site personnel at the study site, and that they will need to bring the 24-hr urine and saliva samples collected on or prior to Day 28 to the study site.

